## **Vitamin C, Hydrocortisone and Thiamine dosing protocol and randomization**

### ***Medication dosing.***

Based on published clinical data, vitamin C pharmacokinetic modeling, the package insert as well as the preliminary study by Marik et al, Vitamin C will be administered as an intravenous dose of 6gm per day divided in 4 equal doses. [22-24,34-37] This dosage is reported to be devoid of any complications or side effects. Hydrocortisone will be dosed according to the consensus guidelines of the American College of Critical Care Medicine.[52] Thiamine will be administered according to current recommendations in a dose of 200mg q 12 hourly. [69]

This is a double-blind placebo controlled study. Only the dispensing pharmacist will be aware of the treatment allocation. Patients will be randomized to receive either vitamin C/hydrocortisone/thiamine or triple placebo using a random number table provided to the dispensing pharmacists. Each patient will be allocated a unique subject ID which will be linked to the randomization sequence. Only the dispensing pharmacists will have a record of the subject ID and randomization sequence. The vitamin C, vitamin C-placebo, hydrocortisone, hydrocortisone-placebo, thiamine, and thiamine-placebo will be formulated as follows:

***Vitamin C:*** Vitamin C is provided by the manufacturer as a 50 ml vial at a concentration of 500mg/ml. Three (3) ml of vitamin C will be placed in a 50 ml bag of Normal Saline (1500 mg vitamin C in 50ml bag) which will then be infused over 30 minutes (100mL/hr). The bag will be labeled by the pharmacy as “Vitamin C 1.5g or Placebo”. The dosing schedule is 1500mg every 6 hours for 4 days (or discontinued earlier if discharged from the ICU).

Once the vial is open, it is only stable for 6 hours. The resulting product is given 12 hour stability. When first ordered, 2 doses are made then and sent to the nurse. For next 12 hours, they will wait until 1 hour prior to make the next batch.

Vitamin C placebo will consist of an identical bag of 50mL normal saline (but with no vitamin C) and will be labeled “Vitamin C or Placebo”. Placebo will be infused over 30 minutes as per the infusion instructions of the active vitamin.

***Hydrocortisone:*** Patients will be treated with hydrocortisone 50mg IV push every 6 hours for 4 days (or discontinued earlier if discharged from the ICU). Pharmacists will prepare hydrocortisone 50mg/1mL for the nurse in a 3mL syringe which will be labeled “Hydrocortisone 50mg or Placebo”. Hydrocortisone placebo will be provided as an identical 3mL syringe as 1mL of normal saline. Two doses of study medication will be prepared at a time.

***Thiamine:*** Intravenous thiamine will be given in a dose of 200mg q 12 hourly for 4 days (or discontinued earlier if discharged from the ICU). This will be placed in a 50mL bag of Normal Saline labeled “Thiamine 200mg or Placebo” and run over 30 minutes (100mL/hr) Placebo patients will receive a matching 50mL bag of Normal Saline. One dose will be prepared at a time.

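### The protocol gives the active and placebo vitamin C bags different label texts, which would be a cue to allocation if printed as written

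*Protocol*

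**What the plan says.** The Protocol's Medication dosing section sets the blinding rule: "This is a double-blind placebo controlled study. Only the dispensing pharmacist will be aware of the treatment allocation". Allocation is all or nothing: "Patients will be randomized to receive either vitamin C/hydrocortisone/thiamine or triple placebo".

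The vitamin C paragraphs of that section then give two label texts. For the bag into which 3 mL of vitamin C has been added, the instruction is "The bag will be labeled by the pharmacy as “Vitamin C 1.5g or Placebo". For the control, "Vitamin C placebo will consist of an identical bag of 50mL normal saline", which the same sentence goes on to qualify: "but with no vitamin C) and will be labeled “Vitamin C or Placebo". The doses leave the pharmacy: "When first ordered, 2 doses are made then and sent to the nurse".

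The other two drugs are handled differently. Hydrocortisone is supplied "in a 3mL syringe which will be labeled “Hydrocortisone 50mg or Placebo", and its control is covered without a second label: "Hydrocortisone placebo will be provided as an identical 3mL syringe as 1mL of normal saline". Thiamine also has one label text, which shows its 200 mg strength and the placebo alternative, and its placebo bag is described as matching.

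The SAP has no text on labels or blinding.

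**The concern.** A masked label works only if it reads the same in both arms. Here the vitamin C label with the strength is tied to the active preparation, and the one without it to the placebo. Anyone following the instruction literally would produce bags whose labels depend on the arm and send them to a nurse who, under the protocol's own rule, should not know the allocation.

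Time to vasopressor independence is listed first among the primary end-points in both the protocol and the SAP. It ends when all pressors are stopped, which is a decision made in the course of care. If those caring for the patient knew the arm, that knowledge could influence when pressors are stopped.

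**Working it through.** No statistical figure is involved. The check is a side-by-side reading of the label instructions in Medication dosing.

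| Study drug | Label given for the active preparation | Label given for the placebo |
|---|---|---|
| Vitamin C | Drug name, 1.5g, placebo alternative | Drug name, placebo alternative, **no strength** |
| Hydrocortisone | Drug name, 50mg, placebo alternative | No separate text; syringe described as identical |
| Thiamine | Drug name, 200mg, placebo alternative | No separate text; bag described as matching |

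**Is the strength on the active label simply a dose error?** No. The preparation text gives 3 mL at 500 mg/mL, and 3 × 500 = 1500 mg = 1.5 g. The label agrees with the preparation. The discrepancy is the presence or absence of the strength.

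**How isolated is it?** The label texts number 2 (vitamin C) + 1 (hydrocortisone) + 1 (thiamine) = 4. Three of the four carry a strength, and the one that does not is the vitamin C placebo label. One drug of three has two texts.

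**Does anything reconcile the two sentences?** The word applied to the placebo bag, identical, could be stretched to include the label. But the same sentence then specifies the label separately and in different words. The section also introduces each active drug and its placebo as separate products to be formulated, so each label sentence attaches to one product. No other part of the protocol, and nothing in the SAP, says that one text is used in both arms.

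**What could be learned if the texts were printed literally?** It depends on the reader.

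- Someone who sees one bag and does not know the pattern learns nothing, since both labels mention placebo.
- Someone who sees bags from patients in both arms could notice two versions. This suggests two groups but does not prove which is active, so the direction must be guessed or learned.
- Someone who knows the protocol wording could identify the arm from the first bag.

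The cue would also recur. Dosing every 6 hours is 4 bags a day, so 4 × 4 = 16 bags over the full 4 days, fewer if the patient leaves the ICU earlier. In a placebo patient, the vitamin C label would lack a strength while the hydrocortisone and thiamine labels showed one. Since allocation is three active drugs or three placebos, decoding one bag decodes the regimen.

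**The case against.** The strongest reply is that the second text is shorthand. Both labels offer placebo as an alternative, a form that makes sense only for a label meant for both arms. The placebo bag is called identical and is infused under the active drug's instructions. The other two drugs follow a one-label scheme, and the section opens with a clear blinding rule. On this reading the strength was dropped when the label was mentioned a second time.

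A second reply is that harm needs a chain of events: literal printing, staff who know or work out the pattern, a correct guess about which version is placebo, and a resulting change in vasopressor decisions. The documents show none of these.

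Both replies have force. The shorthand reading is plausible, and no unblinding can be inferred. What they do not remove is the text itself. The wording differs by arm in an operational instruction to the pharmacy, and a pharmacist following it literally would be complying with the protocol. The benign reading has to be supplied by the reader, because the documents do not state it.

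**Conclusion.** The inconsistency is real and should be corrected. Confidence is high that the two label texts differ by arm and are not reconciled anywhere. That confidence does not extend to any actual unblinding, since the documents do not show what was printed.

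What can be stated is limited: one of three drugs has two label texts, differing only by the strength. The effect on time to vasopressor independence cannot be quantified. It would be nil if the labels printed were the same in both arms. Any effect would require labels that differed, staff who recognised the pattern, and decisions influenced by it. The point weighs more than a typographical slip because it bears on the blinding of a primary end-point that depends on a care decision. It is not a demonstrated flaw in the trial's conduct.

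**What to change.** Amend the vitamin C paragraphs of Medication dosing, and the matching pharmacy instructions, so that they state one label text and say expressly that it is used on active and placebo bags alike. Blinding requires only that the texts be the same. Showing the strength on both would match the pattern already used for hydrocortisone and thiamine.

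Then check pharmacy records for the vitamin C labels actually printed. If they were the same in both arms, say so, and the question is closed. If they differed, correcting the wording cannot restore blinding for patients already treated, and the difference should be disclosed when time to vasopressor independence is interpreted.

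The cost is a one-line correction and a records check, with no extra patients or study time.

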**Power Calculation:**

Based on the results of the preliminary study of Marik et al we project that the combination of hydrocortisone, vitamin C and thiamine could reduce time to vasopressor discontinuation from 54 (+/- 30 hours) versus 30 hours. For the additional primary outcome we projected a greater change of SOFA score of 4 (+/- 3) versus 2. Assuming a type 1 error of 5% (alpha of 0.05) and a power of 80% (the ability to detect a difference between two groups when a difference exists) would require a sample size of 94 patients. To account for dropouts and patients not requiring vasopressor therapy we will therefore aim for a sample size of 140 patients.

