It has previously been suggested that *“...the best hope for therapeutic advances [in sepsis] will depend on broad-base targeting, in which multiple components are targeted at the same time.”*[51] Such combination “chemo-therapy” targeting multiple biological pathways is the standard approach in the treatment of malignant disease. While the benefits of vitamin C, hydrocortisone, and thiamine alone are likely limited,[23,49,50,52] we believe that these medications act synergistically to reduce the risk of organ failure and death in patients with sepsis. This hypothesis is supported previous research [53,54] and more recently a set of elegant experiments performed by Barabutis et al. [55] Using a validated pulmonary endothelial monolayer model, these authors demonstrated that hydrocortisone together with vitamin C protected the vascular endothelium from damage by endotoxin while neither agent alone had this effect. Previous research has demonstrated that vitamin C reverses oxidation of the glucocorticoid receptor (GR) a likely manifestation of sepsis.[53] Oxidation of the GR limits binding of the GR to both ligand and DNA responsive units decreasing the activity of glucocorticoids. [53] Furthermore, glucocorticoids increase the expression of the sodium vitamin C transporter-2 (SVCT-2) which is an essential transport protein necessary for vitamin C to be transported intracellularly.[54]

We therefore propose that a “metabolic resuscitation protocol” including vitamin C, corticosteroids and thiamine will limit the development of organ failure and reduce mortality in patients with severe sepsis and septic shock. This postulate is supported by the preliminary findings by Marik et al. [56] In a retrospective before-after clinical study, these authors compared the outcome and clinical course of consecutive septic patients treated with intravenous vitamin C, hydrocortisone and thiamine during a 7-month period (treatment group) compared to a control group treated in during the preceding 7 months.[56] The primary outcome was hospital survival. A propensity score was generated to adjust the primary outcome. There were 47 patients in both treatment and control groups with no significant differences in baseline characteristics between the two groups. The hospital mortality was 8.5% (4 of 47)

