in the treatment group compared to 40.4% (19 of 47) in the control group ( $p < 0.001$ ). The propensity adjusted odds of mortality in the patients treated with the vitamin C protocol was 0.13 (95% CI 0.04-0.48,  $p=0.002$ ). The SOFA score decreased in all patients in the treatment group with none developing progressive organ failure. Vasopressors were weaned off all patients in the treatment group, a mean of  $18.3 \pm 9.8$  hours after starting treatment with vitamin C protocol. The mean duration of vasopressor use was  $54.9 \pm 28.4$  hours in the control group ( $p < 0.001$ ). The results of this study provide sufficient information for the design of an adequately powered, pragmatic randomized controlled trial.

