**Study end-points:**

***Primary end-point***

- i. Time to vasopressor independence. Defined as the time from starting the active treatment/placebo to discontinuation of all pressors
- ii. Delta SOFA score, defined as the initial SOFA score minus the day 4 SOFA score

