***Data Collection:***

The following de-identified demographic and clinical data will be collected.

- i. Age
- ii. Sex
- iii. Weight
- iv. Admitting diagnosis and possible site of infection
- v. Blood culture results
- vi. Co-morbidities, including diabetes, hypertension, cardiac failure, COPD, malignancy
- vii. Requirement for mechanical ventilation (Y/N).
- viii. Use of vasopressor agents (Y/N). The hourly dosage of vasopressors will be recorded as the norepinephrine equivalent dosage. [70,71]
- ix. Duration of vasopressor use
- x. Time to vasopressor independence from start of active drug/placebo
- xi. Daily urine output (for first 4 days)

xii. Fluid balance after 24 and 72 hours

xiii. Presence of acute kidney injury (AKI). Presence of AKI: Acute kidney injury (AKI) will be defined using the KDIGO criteria; namely, an increase of the s-creatinine > 0.3 mg/dl or a level > 1.5 times the baseline value. [27] If the baseline s-creatinine is not known a value > 1.5 mg/dl will be regarded as diagnostic of AKI.

xiv. Length of ICU and hospital stay

xv. ICU, hospital, and 28-day mortality

xvi. Routine laboratory data for 4 days including:

a. serum creatinine

b. white cell count (WBC)

c. platelet count

d. total bilirubin

e. PaO2/FiO2 ratio

f. Procalcitonin (PCT) – on days 1 and 4

g. lactate level

h. urine oxalate level (day 4)

xvii. HostDx Sepsis genetic testing (day 1) if consent is provided for additional sub-study.

xviii. The patients' admission APACHE II and APACHE IV scores will be recorded. The APACHE IV score allows calculation of the predicted hospital mortality and predicted ICU length of stay (LOS).

ix. The daily SOFA (Sepsis-related Organ Failure Assessment) score will be recorded for the first 4 treatment days.

The APACHE II score (incrementing score of 0-71) and APACHE IV score (incrementing score 0-286) are standardized measures of disease severity that are used to predict hospital mortality and ICU LOS.

[72,73] The SOFA score was designed to sequentially assess the severity of organ dysfunction in patients who are critically ill from sepsis (incrementing score 0-24). [74]. The SOFA scores is calculated 24 hours

after admission to the ICU and daily thereafter. SOFA scores that increase by about 30 percent are associated with a mortality of at least 50 percent.[75]

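### The 54-hour placebo assumption for time to vasopressor independence is a total vasopressor duration, while the end-point counts from the first study dose; the effect on power turns on a clock and a delay the plan does not state

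*Protocol*

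**What the plan says.** The Power Calculation, identical in protocol and SAP, rests its projection on the preliminary before-after study and states that the combination "could reduce time to vasopressor discontinuation from 54 (+/- 30 hours) versus 30 hours". For the second primary end-point, "we projected a greater change of SOFA score of 4 (+/- 3) versus 2". From these it derives 94 patients at alpha 0.05 and 80% power, raised to 140 for dropouts and patients who never need vasopressors.

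The protocol's Background reports the preliminary study on two clocks. Treated patients were off vasopressors a mean of 18.3 ± 9.8 "hours after starting treatment with vitamin C protocol". For controls, "The mean duration of vasopressor use was" 54.9 ± 28.4 hours. The treated patients were "compared to a control group treated in during the preceding 7 months", so no study-drug start is described for the controls.

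Primary end-point i is "Defined as the time from starting the active treatment/placebo to discontinuation of all pressors". Data Collection keeps the two quantities apart: item ix is "Duration of vasopressor use" and item x is "Time to vasopressor independence from start of active drug/placebo".

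**The concern.** The placebo value in the power calculation appears to be a different variable from the end-point it is meant to describe. Time on vasopressors before the first dose counts in the 54.9 hours but not in the end-point. Such time is likely for patients in shock at entry, because consent, compliance with the sepsis bundle, randomisation and pharmacy preparation all come before the first dose. The eligibility criteria limit when sepsis is diagnosed relative to ICU admission; they do not limit the time from vasopressor start to first dose.

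At stake is whether the placebo course, and perhaps the contrast and power built on it, describes what the trial will observe.

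**Working it through.** **Inputs.** From the Power Calculation: 54 versus 30 hours, SD 30; Delta SOFA 4 versus 2, SD 3; alpha 0.05; power 80%; 94 patients. From the Background: controls 54.9 ± 28.4 hours, treated 18.3 ± 9.8 hours. Assumed, because not stated: two-sided test, 1:1 allocation (47 per arm), all 94 patients on vasopressors. The delay d from vasopressor start to first dose is not given, so it is varied.

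**1. The plan's own figure.** n per arm = 2(1.960 + 0.842)² × (SD/difference)².
- Vasopressor time: 15.70 × (30/24)² = 24.5, so 25 per arm, 50 in total.
- Delta SOFA: 15.70 × (3/2)² = 35.3, so 36 per arm, 72 in total.

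Neither gives 94. That is a separate matter; 94 is used below as the plan's number. With 47 per arm and a 24-hour difference, power for end-point i is 97%.

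**2. Where 54 and 30 come from.** 54 (± 30) is close to the control figure of 54.9 (± 28.4), a total duration. The 30 is not the reported treated value of 18.3. Two derivations fit equally well: 18.3 + 11.7 = 30 (an 11.7-hour delay added, making 30 a total duration), or a cautious rounding-up on the first-dose clock. The preliminary contrast is 54.9 − 18.3 = 36.6 hours; the plan uses 24, which is 12.6 hours less.

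**3. Simple subtraction, treated mean held at 30 hours from first dose.** The difference is 54 − d − 30. At d = 6, 8 and 12 hours it is 18, 16 and 12 hours, and power with 47 per arm is 83%, 73% and 49%. The smallest difference with 80% power is 30 × √(2/47) × 2.802 = 17.3 hours, so 80% is lost beyond d = 24 − 17.3 = 6.7 hours.

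**4. Residual-time model.** Subtraction ignores that only patients still on vasopressors at first dose contribute remaining time. Let T be gamma with mean 54.9 and SD 28.4 (shape (54.9/28.4)² = 3.74). The placebo mean from first dose is E[T − d | T > d], the integral of the survival function beyond d divided by its value at d, rescaled by 54/54.9. Power is from the two-sample t test, SD 30, 47 per arm.

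| d (h) | Placebo mean (h) | Treated 30 h: difference, power | Treated 18.3 h: difference, power | Treatment removes 24/54 of remaining time: power |
|---|---|---|---|---|
| 0 | 54.0 | 24.0, 97% | 35.7, >99% | 97% |
| 6 | 48.2 | 18.2, 83% | 29.9, >99% | 93% |
| 12 | 42.9 | 12.9, 54% | 24.6, 98% | 86% |
| 18 | 38.5 | 8.5, 27% | 20.2, 90% | 78% |
| 24 | 35.0 | 5.0, 12% | 16.7, 76% | 70% |

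In the last column, if the treated SD shrinks in proportion to the mean and the model's own residual SD is used, power is about 99%, 98% and 93% at 6, 12 and 24 hours.

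**5. Both figures as total durations.** If 30 hours is a total duration and the delay is equal in both arms, the difference is (54 − d) − (30 − d) = 24 hours at any d, and the requirement stays at 50.

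**The case against.** A reader might infer that 54 versus 30 mixes two clocks, and that the 24-hour contrast and the 80% power are therefore overstated. The documents do not support that as a fact. The 30 hours has no stated source or clock. The planned contrast is already 12.6 hours below the preliminary one. The only treated mean that the documents place on the end-point's clock is 18.3 hours, and with it 80% power survives a delay of 18 hours. The steep loss appears only if the sponsor's more cautious 30 hours is kept and the control figure alone is shortened. The modelling also gives every patient the same delay and has everyone on vasopressors before the first dose, although the trial also admits sepsis without shock. All of this stands.

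It can also be said that Delta SOFA drives the sample size (72 against 50). Under step 3 that holds only to about 4 hours of delay, where the vasopressor end-point also needs 72; at 6 hours it needs 88.

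The 12.6-hour margin is not a full answer. No document says it allows for pre-dose time, and the discount was made on the treated side (18.3 to 30) while the control figure stayed near 54.9. Under every reading, 54 hours remains a total duration.

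A reader might also infer that eligibility needs an upper limit on time to first dose. The documents give no figure on how many patients that would affect or what it would gain, so this point does not support one.

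**Conclusion.** The concern holds for the input and only conditionally for the power. The placebo mean and SD for primary end-point i derive from total vasopressor duration in historical controls who had no study-drug start, whereas the end-point runs from the first study dose. If vasopressors precede that dose, 54 hours is too long for the placebo arm on the end-point's clock: about 48 hours at a 6-hour delay and 43 at 12, under the gamma assumption.

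The consequence for power ranges from none (both figures total durations, equal delay) to a fall below 80% beyond about 7 hours (treated mean fixed at 30 hours from first dose). With a treated mean of 18.3 hours, the 80% is lost only somewhere between 18 and 24 hours. The documents give neither the clock nor the delay needed to choose among these. All figures assume SD 30 unless stated, 47 per arm and a two-sided test.

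**What to change.** 1. In the Power Calculation of both documents, state the source and clock of the 30 hours. Replace 54 (± 30) with a placebo mean and SD counted from first dose, and restate the power over a stated range of delays. This is wording only; the stated power may become less favourable.

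2. Derive each patient's pre-dose vasopressor time from the hourly vasopressor doses already recorded (Data Collection, item viii), and pre-specify it as a baseline covariate for end-point i. Do not simply take item ix minus item x: that fails when vasopressors are restarted or first begun after the first dose. The Data analysis section names only unadjusted tests, so a regression model would have to be added. Expect a small gain in precision: R² is about 4% if the delay is uniform over 0 to 24 hours. Randomisation already balances pre-dose time in expectation, so this is a refinement and not a correction of bias.

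Neither change needs new data, visits or patients.

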***Data analysis:***

Summary statistics will be used to describe the clinical data and presented as mean  $\pm$  SD, median with interquartile range (IQR) or percentages as appropriate. Chi squared analysis with Fisher’s exact test (when appropriate) and Student’s t test (Mann Whiney U test for non- normal distributions) were used to compare data between the active treatment group and the placebo group with statistical significance declared for probability values of 0.05 or less.

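### The sample size of 94 does not follow from the inputs stated with it, which give 52 and 74; the discrepancy is conservative, but its basis is not disclosed.

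*Protocol*

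**What the plan says.** The Power Calculation section of the protocol, repeated word for word in the SAP, sizes the trial in one paragraph. For the first primary end-point the combination "could reduce time to vasopressor discontinuation from 54 (+/- 30 hours) versus 30 hours". For the second, it projects a SOFA change of 4 against 2, with 3 after the plus/minus sign. The error rates follow: "Assuming a type 1 error of 5% (alpha of 0.05) and a power of 80" per cent. The paragraph then gives a single total: this "would require a sample size of 94 patients". A last step raises it: "To account for dropouts and patients not requiring vasopressor therapy we will therefore aim for a sample size of 140 patients".

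The paragraph names no test, sidedness, allocation ratio or end-point for the 94. Elsewhere, Data analysis names Student's t test, or the "Mann Whiney U test for non- normal distributions", with "statistical significance declared for probability values of 0.05 or less". The randomization text says that patients are allocated "using a random number table provided to the dispensing pharmacists" and gives no ratio.

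**The concern.** All the numerical inputs to a two-sample comparison of means are given, so a reader should be able to recover 94. The standard calculation gives two other numbers, both well below it. A total that cannot be rebuilt from its own inputs leaves three things open: which of the two primary end-points it protects, what power the trial has for each, and whether an input was used that the text does not mention. The 94 is also the base for the 140 to be recruited, so anything hidden in it carries through to the recruitment target.

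**Working it through.** **Inputs (Power Calculation).** Vasopressor time: difference 54 − 30 = 24 h, SD 30, so d = 24/30 = 0.80. SOFA change: difference 4 − 2 = 2, SD 3, so d = 2/3 = 0.667. Alpha 0.05, power 0.80. Assumed because not stated: two-sided t test, 1:1 allocation, and the plus/minus figure as an SD common to both arms.

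**Attempt to reproduce 94.** Normal approximation: n per arm = 2(1.960 + 0.842)²/d² = 15.70/d².
- Vasopressor time: 15.70/0.64 = 24.5, so 25 per arm, 50 in total.
- SOFA change: 15.70/0.444 = 35.3, so 36 per arm, 72 in total.

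Exact t test (noncentral t):
- Vasopressor time: 25.5, so 26 per arm, **52** in total.
- SOFA change: 36.3, so 37 per arm, **74** in total.

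Neither is 94, and the gap is too large for rounding or choice of approximation.

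**Other readings at the same alpha and power.**

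| Reading | Vasopressor time | SOFA change |
|---|---|---|
| One-sided t test | 42 | 58 |
| 2:1 allocation, t test | 60 | 84 |
| Mann-Whitney, efficiency 0.955 | 54 | 78 |
| Mann-Whitney, lowest efficiency 0.864 | 60 | 86 |

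- Joint power of 80% on both end-points, treated as independent: at 41 per arm the powers are 0.947 and 0.847, product 0.802, so 82 in total.
- Event-based sizing with an assumed hazard ratio of 30/54 = 0.556: the Schoenfeld formula gives 4 × 7.849/(ln 0.556)² = 90.9, so 91 events. The Freedman formula gives 7.849 × (1.556/0.444)² = 96.1, so 97 events. These are events, not patients, and neither is 94.

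**What does reach 94.** Each route needs something the paragraph does not say. Two examples:
- SOFA change at alpha 0.025 (half of 0.05) with Mann-Whitney inflation: 44.05/0.955 = 46.1, so 47 per arm, 94 in total.
- SOFA change at alpha 0.05 inflated for an assumed 20% loss: 37/0.8 = 46.25, so 47 per arm, 94 in total.

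As a third, 90% power for SOFA change comes near: 96 by the normal approximation, 98 by the t test. Several unrelated routes end at or near 94, so the number alone does not identify its origin.

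**Power that 94 evaluable patients give** (47 per arm, two-sided t test, alpha 0.05): 0.970 for vasopressor time and 0.892 for SOFA change.

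**The case against.** The strongest reply is that nothing is harmed. The 94 exceeds both requirements, the target of 140 is larger still, and no enrolment or analysis rule depends on how 94 was obtained. That stands, and it limits the point to a correction of the text. It does not make 94 and 80% consistent with the inputs beside them.

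It can also be said that the test is known, because Data analysis names it. That is partly right. That section offers a t test or a rank test depending on the distribution, and the power paragraph does not say which it used. Neither gives 94.

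Some stronger readings are tempting and should not be drawn:
- *Alpha is missing, or conflicts with the analysis.* It is stated as 0.05 in the same sentence as the 94, and Data analysis uses the same threshold. Only sidedness and any division between the two primary end-points are unstated. The 0.025 route is a guess that happens to land on 94; no text supports it.
- *Dropouts were counted twice.* This would follow only if the 20% inflation was the route used, and the documents do not say so.
- *The trial is underpowered.* On the stated inputs the opposite holds.
- *The 54 h input comes from a different clock and so removes power.* The input does resemble a pilot control figure in Background and Significance ("The mean duration of vasopressor use was" 54.9 ± 28.4 h), whereas the end-point counts from the first study dose. The documents give no interval between vasopressor start and first dose. It could be zero, so no loss of power can be derived from it.

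**Conclusion.** The point holds as an unreproducible figure with an undisclosed derivation, which is not the same as a proven slip in calculation. On the stated alpha and power the requirements are 52 and 74, so 94 is 42 above the first and 20 above the second. If all 94 are evaluable for both end-points, the powers are about 97% and 89%, so the stated 80% describes neither. These figures rest on a two-sided t test, 1:1 allocation and a common SD; the other readings checked change the requirements but none yields 94. The direction is conservative and the target of 140 is not called into question.

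**What to change.** Keep 140 and correct the Power Calculation paragraph in both documents:

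1. Replace the single statement of 94 at 80% power with the requirement for each end-point (52 for vasopressor time, 74 for SOFA change) and the power that 94 evaluable patients give (97% and 89%).
2. Name the test, the sidedness and the allocation ratio used for sizing.
3. If 94 came from a further input, such as a divided alpha or a dropout inflation, state it. Make it agree with the 0.05 threshold in Data analysis and with the later increase to 140.
4. At most, add one sentence noting that the 54 h assumption resembles the pilot's duration of vasopressor use, while the end-point counts from the first study dose.

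The cost is one reworded paragraph in each document, with no extra patients and no new data. If the original derivation cannot be recovered, the first two items are enough.
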